5. KNOWN TOXICITIES AND DOSE ADJUSTMENTS

5.1. KNOWN TOXICITIES OF IDELALISIB

Idelalisib is FDA approved for the treatment of relapsed chronic lymphocytic leukemia/small lymphocytic lymphoma and follicular B-cell non-Hodgkin lymphoma. Idelalisib may cause:

- ALT/AST elevations and hyperbilirubinemia (most frequently occurs within the first 12 weeks of treatment); incidence of serious hepatotoxicity: 14.0%
- Diarrhea (mean time to occurrence 7.2 months); incidence of serious/severe diarrhea: 14.0%
- Pneumonitis; incidence <5%
- Neutropenia: Grade 3 or 4 neutropenia occurs in approximately 31% of patients receiving the 150mg bid dose.
- Rash: Grade 3 or 4 rash occurred in approximately 21% of patients receiving the 150mg BID dose.
 - CYP3A affects: CYP3A inducers can reduce the AUC of idelalisib by 75%; CYP3A inhibitors can increase the AUC of idelalisib by 1.8 fold; idelalisib is strong CYP3A inhibitor. A list of these drugs can be found in appendix 4. Importantly, with direct relevance to this study is the lack of data supporting strong interaction with voriconazole. Azoles are often the medication of choice for patients with suspect fungal or anti-bacterial non-responsive fevers during alloBMT. The elimination of idelalisib is predominantly mediated by the hepatic pathway. Idelalisib is primarily metabolized by aldehyde oxidase with a lesser involvement of cytochrome P450. The major metabolite of idelalisib is GS-563117. Data indicate that CYP3A inhibition by concurrent use of azoles may result in modestly higher exposures of idelalisib, but the change is not of clinical relevance²¹. In this study, as the dosing of idelalisib is already reduced to 100mg bid to provide additional risk mitigation. Additionally, patient's receiving azole therapy while on idelalisib will have serum levels monitored to adjust to target levels.

Therefore, to protect patients in this study the following measures are employed:

- Patients will have comprehensive metabolic panels performed every 2 weeks through day +120, then monthly through day +270.
- Patients post alloBMT may develop intestinal aGVHD which may present with diarrhea or ileus. All patients with ≥ 3 grade diarrhea will also be evaluated for aGVHD in addition to idelalisib dose modification.
- Patients post alloBMT may develop aGVHD which often presents with a generalized cutaneous rash. All patients with ≥ 3 grade rash will also be evaluated for aGVHD in addition to potential idelalisib dose modification.
- Patients post alloBMT often develop late neutropenia after achieving neutrophil recovery. To help limit the depth of neutropenia that could be attributable idelalisib, idelalisib will be dosed at 100mg bid, the suggested dose reduction for patients experiencing an ANC $< 5 \times 10^9/L$ while on the standard 150mg bid dosing schedule
- CYP3A interactions. Commonly, patients post alloBMT require azole based antifungal prophylaxis and/or treatment. Patients receiving posaconazole or voriconazole will have these levels checked every 14 days while receiving idelalisib.
- Additionally, in the post alloBMT patient population, novel toxicities need to be considered, therefore, stopping rules will be established to stop this study, if compared to the placebo control the incidence of GVHD or any other toxicity caused by idelalisib or placebo causes discontinuation at a rate differential of $>10\%$.

5.2. DOSE ADJUSTMENT OF IDELALISIB OR PLACEBO

Study drug consists of oral idelalisib or placebo tablets. The standard dose of idelalisib for this protocol is 100mg idelalisib tablets (orange, oval shaped and film coated) or matched 100mg silicified microcrystalline cellulose placebo tablets taken twice a day.

When necessary, idelalisib or matched placebo dose can be adjusted to 100 mg taken once a day. Based on current PK data supplied by Gilead, a clinical trial examining various idelalisib doses in combination with a second drug held at a fixed dose found that the steady state AUC for idelalisib 100 mg QD dosing reduced patient idelalisib exposure by ~30% as compared to 50 mg BID dosing. The investigators further determined that the second drug did not influence the idelalisib drug concentrations at the studied doses. Additionally, Gilead study 101-02 demonstrated AUC_{0–24h} were similar, 19,600 and 16,300 ng.h/mL for 150mg BID and 300mg QD, respectively.²¹ Due to this data, we are confident that a dose reduction from 100mg BID to 100mg tablets taken once daily will sufficiently reduce patient exposure to idelalisib in the context of this study.

PNEUMONITIS

Non-infectious pneumonitis can occur with Idelalisib use and occurs in allogeneic bone marrow transplant recipients. A diagnosis of non-infectious pneumonitis should be considered in patients presenting with non-specific respiratory signs and symptoms such as hypoxia, pleural effusion, cough or dyspnea, and in whom infectious, neoplastic and other non-medicinal causes have been excluded by means of appropriate investigations. Opportunistic infections such as PJP should be ruled out in the differential diagnosis of non-infectious pneumonitis. Patients should be advised to report promptly any new or worsening respiratory symptoms.

If idiopathic, symptomatic pneumonitis occurs, stop study drug until symptoms resolve to less than or equal to grade 1. The use of corticosteroids may be indicated. Study drug may be reintroduced at a dose of 100 mg once daily. If idiopathic pneumonitis recurs at the reduced dosing level, then discontinue study drug permanently.

HEPATOTOXICITY

Transaminitis and hyperbilirubinemia can occur with idelalisib use and are also common in allogeneic bone marrow transplant recipients. For patients experiencing an AST/ALT or bilirubin >5x ULN that is unexplained by other factors, hold study drug until the parameter is \leq 2ULN and restart at 100mg once daily. If the parameter should rise again >5 ULN, discontinue study drug. For AST/ALT >20x ULN (or Bilirubin >10x ULN), regardless of attribution, study drug should be permanently stopped.

DIARRHEA

Diarrhea can occur with idelalisib use and is also common in allogeneic bone marrow transplant recipients. Prior to major pharmacologic intervention, common infectious causes of loose stooling should be evaluated. For loose stools, in the absence of major infections, anti-motility agents may be offered and/or light steroid preparations. For patients with significant stooling, >1L daily, hold study drug and consider colonic biopsy if there is evidence to suggest aGVHD. Once stooling is <0.5L day, restart at 100mg oncedaily. If stooling should

again increase to >1L daily, discontinue study drug. For life-threatening diarrhea, study drug should be permanently stopped.

NEUTROPENIA AND THROMBOCYTOPENIA

Neutropenia and thrombocytopenia can occur with idelalisib use and are also common in allogeneic bone marrow transplant recipients. For ANC < 500 or PLT < 25,000, monitor CBC with differential weekly, hold study drug until ANC >1,000 and PLT count >50,000 and restart at the original dose. If a subject develops ANC < 500 or PLT < 25,000 a second time, hold study drug until ANC >1,000 and PLT count >50,000 and restart at 100mg once daily. If a subject who is on 100mg once daily develops ANC < 500 or PLT < 25,000, discontinue study drug.

Acute GVHD: Patients with symptomatic aGVHD will be treated as per institutional guidelines. If after seven days of therapy there is evidence of progressive aGVHD, study drug will be stopped for at least seven days. If it is determined that study drug was not causative of the aGVHD it may be restarted at the discretion of the primary oncologist. If after 14 days of active therapy there is no improvement of the aGVHD, study drug will be stopped for at least seven days. If it is determined that study drug was not causative of the aGVHD persistence it may be restarted at the discretion of the primary oncologist.

LATE ONSET NEUTROPENIA (LON)

Rituximab-associated LON is defined by most investigators as grade III-IV neutropenia (ANC <500 cells/ μ L), occurring after the ANC has recovered to within normal limits, but within 3-4 weeks after the last dose of rituximab²². If subject develops LON after rituximab use or which per medical judgement can be attributed to another cause outside of the use of idelalisib, the subject may receive the appropriate medical or surgical intervention without being taken off study or having study drug held. If, in the judgment of the attending physician, the subject has had no resolution of symptoms after receiving standard intervention, study drug will be held until ANC >1000.

6. STUDY STATISTICS

This is a phase I study of Idelalisib, an orally-administered, selective inhibitor of Phosphoinositide 3 kinase (PI3K)- δ . It has been successfully used pre-transplant to induce partial and complete responses in many B-cell derived malignancies. In this study Idelalisib will be evaluated in the post-transplant setting. Patients receiving a standard of care allogeneic hematopoietic stem cell transplant from any source: cord, marrow, or peripheral blood will be eligible. Patients will be randomized in a 2:1 ratio to either 100 mg Idelalisib twice daily from day 90 (\pm 10 days) following transplant, Arm A, or a placebo, Arm B, and monitored for toxicity until day 270.

Study treatment plan: Idelalisib day +90 [+/- 10 days), 100mg twice daily, and at least 5 days after the discontinuation of filgrastim if ANC is greater than 1,000 and PLT 50>Gi/L and <grade 2 aGVHD. Patient's Idelalisib will be dose adjusted for the expected toxicities of Idelalisib including pneumonitis, hepatitis, neutropenia, thrombocytopenia and loose stools.

Primary endpoint and design: The primary goal of this study is to evaluate the safety of Idelalisib as post-transplantation maintenance in patients undergoing an allogeneic BMT. In addition to the allowed dose reductions, a safety monitoring plan will be implemented to ensure that other treatment-limiting events are not elevated. The study will be monitored between the date of randomization and day 270 post-transplant. For safety monitoring, treatment-limiting toxicities will be defined as Idelalisib interruption for >14 days, or other grade 3 or higher adverse events as defined by CTCAE IV not captured in the protocol for dose de-escalation. The trial will assume that, *a priori*, the probability of these events in both arms of the study will follow a Beta (0.10, 0.90) prior distribution. This distribution corresponds to an assumption that 10% of patients might experience a treatment-limiting toxicity.

Sample size/accrual Rate: The accrual rate for this study is expected to be 20 patients per year. The total sample size will be 45 patients, 30 on the Idelalisib arm (Arm A) and 15 on the control arm (Arm B). The safety objective of this trial is based on the precision of estimating the specified treatment-limiting toxicity events. An approximation to the precision will be made using binomial confidence intervals. Thirty patients on the Idelalisib arm will allow us to estimate the proportion of patients experiencing post-transplant events with a precision of $\pm 0.19\%$.

Interim analyses and operating characteristics: For monitoring we will compute the posterior probability of a treatment-limiting toxicity between day 90 and 270 in each arm of the study, given the data and prior distribution, Beta(0.10, 0.90), and evaluate whether to hold accrual after fixed cohorts of patients. Monitoring will occur in groups of 15 patients, beginning after the first 10 enrolled on Arm A. The maximum sample size will be 45 patients, 30 in Arm A and 15 in Arm B. The stopping rule will recommend a safety review if it becomes clear that the posterior probability of a treatment-limiting toxicity in Arm A exceeding Arm B by 0.10 is 75% or greater. Operating characteristics of the study with Arm B treatment-limiting toxicity of either 5%, Table 1, or 10%, Table 2, and varying toxicities in Arm A are based on 1,000 simulations of the trial.

Table 1. Scenarios with control arm (Arm B) treatment-limiting toxicity of 5%
Both arms prior: Beta (0.10, 0.90), assumes prior for toxicity is 10%, delta of 0.10, and 75% cutoff.
2:1 randomization Total N=45

	Delta=0.10	Delta=0.10
Scenario: Control, Idelalisib	Stopped for toxicity	Avg. sample size Control, Idelalisib
1: 0.05, 0.05	1.3%	14.9, 29.8
2: 0.05, 0.10	6.8%	14.4, 28.8
3: 0.05, 0.15	19.2%	13.4, 26.8
4: 0.05, 0.20	32.4%	12.3, 24.7
5: 0.05, 0.25	53.1%	10.5, 21.0
6: 0.05, 0.30	68.2%	9.3, 18.7
7: 0.05, 0.35	82.3%	8.0, 16.0
8: 0.05, 0.40	89.8%	7.1, 14.2
9: 0.05, 0.45	94.9%	6.3, 12.6

Table 2.

Scenarios with control arm (Arm B) treatment-limiting toxicity of 10%

Both arms prior: Beta(0.10, 0.90), assumes prior for toxicity is 10%, delta of 0.10 and 75% cutoff.

2:1 randomization Total N=45

	Delta=0.10	Delta=0.10
Scenario: Control, Idelalisib	Stopped for toxicity	Avg. sample size Control, Idelalisib
1: 0.10, 0.10	4.9%	14.6, 29.1
2: 0.10, 0.15	12.0%	13.9, 27.8
3: 0.10, 0.20	27.9%	12.7, 25.4
4: 0.10, 0.25	44.3%	11.4, 22.8
5: 0.10, 0.30	59.0%	10.1, 20.2
6: 0.10, 0.35	70.7%	9.3, 18.5
7: 0.10, 0.40	83.4%	8.1, 16.1
8: 0.10, 0.45	90.0%	7.3, 14.5
9: 0.10, 0.50	94.4%	6.6, 13.1

Secondary endpoint:

1. Event-free survival at one year.

Analysis Plans:

Toxicities will be summarized descriptively by grade and type. Cumulative incidences of aGVHD, relapse, and NRM will also be computed using Fine and Gray's method for competing risks. Treatment of relapse/progression, graft failure, and death are considered competing risks for GVHD; relapse/progression is a competing risk for NRM; and death before relapse/progression is a competing risk for relapse/progression. In addition, we plan to report aGVHD incidences with only graft failure and death regarded as competing risks.

Using the Kaplan-Meier method, the probability of 1-year event-free survival will be estimated and reported with 95% confidence intervals. The proportions of patients who are event-free at 1 year will also be estimated with a 95% exact binomial confidence interval.

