1. INTRODUCTION

For all relapsed B cell derived hematologic malignancies, allogeneic bone marrow transplantation (allo BMT) is often the most definitive curative intent therapy. Historically, there have been four obstacles decreasing overall survival (OS) associated with allo BMT: preparative conditioning toxicity, donor availability, graft-versus-host-disease (GVHD) and disease relapse. Reduced intensity conditioning (RIC) regimens have dramatically reduced alloBMT toxicity and have expanded the use of this therapy to patients up to 75 years of age.(1-3) The use of alternative donors has resulted in an average of 2.7 donors for each patient in Johns Hopkins University.(4) The use of post-transplant cyclophosphamide has reduced the incidence of Grade III-IV GVHD to 6% - 11%.(5-7) However, disease relapse after successful engraftment during allo BMT remains the limiting factor for improving overall survival. (5, 6, 8)

Currently, in order to improve OS, the BMT program at JHH has recently focused on the introduction of anti-neoplastic therapy post transplantation. We use the allo HSCT as a platform to allow a new intolerant immune system to interact with a post allo HSCT biologic or therapeutic intervention. Currently, to improve overall survival, the focus of the BMT program at JHH the introduction of anti-neoplastic therapy post transplantation: where the allo BMT serves as a platform to allowing a new intolerant immune system to interact with the post allo BMT intervention. The importance of post BMT therapy has been made evident with tyrosine kinase inhibition (TKI) in Ph+ ALL and Ph+ CML, where patients who had disease progression while on TKI therapy pre-allo BMT enjoy marked improvement in OS when TKI is part of a maintenance program (9-12); the use of DNA hypomethylation agents after allo BMT for relapsed myeloid malignancies (13); or the use of rituximab after allo BMT in follicular lymphoma (PMID 26183076). At JHH we are currently, utilizing post allo BMT: TKI in Ph+ leukemia's, sorafenib and other multi-kinase inhibitors in FLT3-ITD AML, and 5-azacytidine in MDS patients.

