9.3.2 Severity of Adverse Events to be collected

All AE grades will be defined per NCI-CTCAE version 4.0 criteria unless otherwise specified starting at the beginning of Idelalisib treatment

With the following exceptions, all AEs of grade 3 or higher will be collected from the time at which the participant receives the first dose of study medication as specified in section 9.4 until the time the participant completes or prematurely withdraws from the study:

- Haematological abnormalities will be collected as AEs per NCI-CTCAE v. 4.0 criteria once participants have achieved platelet and neutrophil recovery.
- All episodes of allograft failure and of acute, grade III or IV GVHD will be collected as AEs.

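### The treatment-limiting toxicity definition does not settle whether grade III-IV acute GVHD counts, although Sections 5.1 and 8.2 present GVHD as a target of the stopping rule

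*Combined protocol and SAP*

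**What the plan says.** **TLT definition.** Sections 4 and 6 are the only places that define a TLT. The first limb in Section 6 concerns time off study drug: "treatment-limiting toxicities will be defined as Idelalisib interruption for >14 days". A second limb adds certain severe events and carries an exemption: "or other grade 3 or higher adverse events as defined by CTCAE IV not captured in the protocol for dose de-escalation". The toxicities that Section 6 lists for dose adjustment are the "expected toxicities of Idelalisib including pneumonitis, hepatitis, neutropenia, thrombocytopenia and loose stools". Acute GVHD is named neither in the definition nor in that list.

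**Section 5.2 (dose adjustment).** There is a separate aGVHD paragraph: "If after seven days of therapy there is evidence of progressive aGVHD, study drug will be stopped for at least seven days". A second hold applies if there is no improvement after 14 days of therapy. Restart is allowed if study drug is judged not to be the cause. The paragraph has no reduced-dose step.

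**Section 5.1.** Stopping rules are promised if, compared with placebo, "the incidence of GVHD or any other toxicity caused by idelalisib or placebo causes discontinuation" at a rate differential above 10%.

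**Section 8.2.** Acute GVHD is one of two novel toxicities named. The section says the Section 6 stopping rules will be followed.

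**Section 9.3.2.** "All episodes of allograft failure and of acute, grade III or IV GVHD will be collected as AEs". It does not say that they are TLTs.

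**Appendix 1.** aGVHD is graded by organ stage and overall grade, whereas the second limb of the TLT definition uses CTCAE grade.

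**The concern.** The TLT is the event behind the prior, the precision statement, the stopping rule and Tables 1 and 2. The protocol itself gives reasons to watch GVHD closely: the Introduction says that PI3K blockade could alter its incidence, and Section 7.1 hypothesises an effect on GVHD. A reader who follows Section 8.2 to Section 6 finds a rule that does not mention GVHD and an exemption that might cover it. Two people classifying the same grade III case could reach different answers, and the chance that the rule reacts to an excess depends on which answer is used.

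**Working it through.** **1. The text on each side**

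| Points towards counting | Points towards exemption |
|---|---|
| aGVHD is absent from the dose-adjusted toxicities listed in Sections 4 and 6 | The aGVHD hold-and-restart rule sits in the dose-adjustment section, 5.2 |
| The Section 5.2 aGVHD rule has no reduced dose, so it is arguably not de-escalation | Loose stools are on the list. The Section 5.2 stool hold starts above 1 L/day; Appendix 1 gut stage II is above 1000 ml/day and falls in overall grade III |
| Section 9.3.2 collects grade III-IV aGVHD as AEs | aGVHD is graded by Appendix 1 and the TLT by CTCAE, with no link between them |

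On the exempt reading, a severe case enters only through the interruption limb (more than 14 days). The aGVHD hold has a minimum of seven days, so some cases would enter and some would not.

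**2. The rule as printed in Section 6**

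Independent Beta(0.10, 0.90) priors; fire when P(pA − pB > 0.10 | data) ≥ 0.75; looks at 10/5 and 20/10 patients (Arm A/Arm B). A third look at 30/15 falls at full enrolment, so results are given for two looks, with three in brackets. Outcomes are taken as complete at each look. For example, with no events in 5 on Arm B, 2/10 on Arm A gives 0.71 (no alarm) and 3/10 gives 0.90 (alarm).

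**3. Check against the plan's own tables**

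| Control, idelalisib | Printed | Exact enumeration |
|---|---|---|
| 0.05, 0.05 | 1.3% | 1.5% (1.9%) |
| 0.05, 0.20 | 32.4% | 46.2% (58.6%) |
| 0.10, 0.10 | 4.9% | 7.3% (9.1%) |
| 0.10, 0.30 | 59.0% | 62.7% (73.0%) |

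The printed rule does not reproduce Tables 1 and 2. The standard error from 1,000 simulations is at most about 1.6 points, so simulation noise does not explain the larger gaps. The results below describe the rule as printed and are illustrative.

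**4. Effect of counting aGVHD**

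Assumptions: a non-GVHD TLT rate of 10% in both arms, independent of aGVHD. The Introduction's 6-11% for grade III-IV GVHD covers the transplant course; the share after day 90 is not given, so the aGVHD rates are also assumed.

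TLT rate = 1 − (1 − base)(1 − counted aGVHD rate)

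- 6% vs 26%, all counted: 1 − 0.90×0.94 = 15.4%; 1 − 0.90×0.74 = 33.4%
- Half counted (3% vs 13%): 1 − 0.90×0.97 = 12.7%; 1 − 0.90×0.87 = 21.7%
- None counted: 10% in both arms
- 6% vs 18%, all counted: 15.4%; 1 − 0.90×0.82 = 26.2%

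| aGVHD, placebo vs idelalisib | Counted | Rule fires |
|---|---|---|
| 6% vs 26% | all | 57% (66%) |
| 6% vs 26% | half | 34% (41%) |
| 6% vs 26% | none | 7% (9%) |
| 6% vs 18% | all | 40% (47%) |
| 6% vs 16% | all | 35% (42%) |

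With a 20-point excess and placebo aGVHD of 3-11%, the all-counted figure stays at 55-57% (65-67%). With a 5% base and 6% vs 26%, it is 60% (70%) if all count and 1.5% (1.9%) if none does.

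**5. The same comparison from the printed tables**

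Non-GVHD rates of 5% and 5% stop 1.3% of trials. Counting aGVHD of 6% vs 26% gives 1 − 0.95×0.94 = 10.7% and 1 − 0.95×0.74 = 29.7%, close to the 0.10, 0.30 row, which stops 59.0%. The direction and rough size therefore do not depend on the mismatch in step 3.

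**6. False alarms if aGVHD counts (10% base, no difference between arms)**

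| aGVHD in both arms | TLT rate | Rule fires |
|---|---|---|
| not counted | 10.0% | 7% (9%) |
| 3% | 12.7% | 11% (13%) |
| 6% | 15.4% | 14% (17%) |
| 11% | 19.9% | 18% (21%) |

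**The case against.** The strongest reply is that Section 6, read on its own terms, already counts severe aGVHD. The exemption concerns de-escalation, the aGVHD paragraph contains no lower dose, and aGVHD is not among the listed toxicities. Section 8.2 then places aGVHD under the Section 6 rule. This stands as the more natural reading, but it remains an inference and does not resolve the overlap with loose stools or the difference in scales.

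Three stronger readings are tempting, and the documents do not support them:

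- *The sections contradict each other on TLT status.* Sections 5.1, 5.2, 8.2 and 9.3.2 give aGVHD no TLT status. The boundary is unstated; there are no opposite statements.
- *On the exempt reading, severe aGVHD that responds to therapy can never be a TLT.* A gut grade III case above 1 L/day triggers the stool hold in Section 5.2, and any hold longer than 14 days counts. Restart after an aGVHD hold also depends on a judgement that study drug was not the cause, so progressive or non-improving cases attributed to the drug would tend to count. The none-counted figure is therefore a lower bound.
- *The trial would not see GVHD.* It is assessed at scheduled visits and collected as an AE, its cumulative incidence is reported, and the Safety Monitoring Committee reviews all data. What is exposed is the TLT endpoint and its formal trigger.

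It is also fair to object that no passage supports a 20-point excess. At 6% vs 18%, a tripling, the rule fires in only 40% (47%) of trials even when every case counts.

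**Conclusion.** The point holds as an unresolved definition that should be settled. The text leans towards counting grade III-IV aGVHD but permits exempting it, in which case a severe case counts only through an interruption of more than 14 days. For 6% vs 26%, the chance of an alarm runs from 57% (66%) with all cases counted down towards 7% (9%), with 34% (41%) if half count. These figures rest on an assumed 10% non-GVHD rate, independence of the two event types, assumed post-day-90 aGVHD rates, an assumed excess, and a printed rule that does not reproduce Tables 1 and 2. They show how much the definition matters and do not predict what this trial will see.

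**What to change.** In Sections 4 and 6, state that new or worsening Appendix 1 grade III-IV acute GVHD after first dose counts as an event for the safety-monitoring rule and is not removed by the dose de-escalation exemption. Align the references in Sections 5.1, 5.2, 8.2 and 9.3.2 with that statement. Rerun Tables 1 and 2 with control rates that include aGVHD (12.7-19.9% under the assumptions above). Treatment and holding rules stay as they are.

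The cost is wording and a simulation rerun, since aGVHD is already assessed and grade III-IV cases are already collected. There is a statistical price: with equal aGVHD of 3-11% in both arms, false alarms rise from about 7% to 11-18% at two looks (9% to 13-21% at three). Under Section 6 the consequence of an alarm is a recommended safety review. If the sponsor prefers not to count aGVHD, Sections 4 and 6 should say so, and Sections 5.1 and 8.2 should no longer imply that the Section 6 rule covers it.

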4. STUDY PROCEDURES

- Idelalisib, 100mg twice daily, starting day +90 (+/- 10 days) and at least five days after the discontinuation of filgrastim, if ANC greater than 1000 and PLT $50 > \text{Gi/L}$ and continued through day +270. Patients will have a CBC with platelet count and comprehensive metabolic panels performed every 14 days beginning at day +90 through day +120, then monthly through day +270.

Patients will be monitored for treatment-limiting toxicities defined as Idelalisib interruption for >14 days, or any other Grade 3 or higher adverse events as defined by CTCAE IV not captured in the protocol for dose de-escalation. All Adverse events will be collected and assessed for causality but only AEs Grade 2 and higher will be recorded on the Master AE log. Patient's idelalisib will be dose adjusted for the expected toxicities of idelalisib including pneumonitis, hepatitis, neutropenia, thrombocytopenia and loose stools.

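### The treatment-limiting toxicity definition has no grade ceiling on its exemption and names neither death nor permanent discontinuation, so a rapidly fatal or late listed toxicity can be scored as no event

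*Combined protocol and SAP*

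**What the plan says.** Section 6 (Primary endpoint and design) gives the monitored event two limbs: "treatment-limiting toxicities will be defined as Idelalisib interruption for >14 days, or other grade 3 or higher adverse events as defined by CTCAE IV". The second limb is restricted to events outside the dose de-escalation provisions; in full it covers "other grade 3 or higher adverse events as defined by CTCAE IV not captured in the protocol for dose de-escalation". Section 4 repeats this in nearly the same terms: "treatment-limiting toxicities defined as Idelalisib interruption for >14 days, or any other Grade 3 or higher adverse events", with the same restriction.

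Section 6 names the toxicities handled by dose adjustment as the "expected toxicities of Idelalisib including pneumonitis, hepatitis, neutropenia, thrombocytopenia and loose stools". Section 5.2 has a rule for each. Some of its rules hold the drug and allow a restart; others end treatment. For extreme liver values it says "regardless of attribution, study drug should be permanently stopped", and for diarrhea "For life-threatening diarrhea, study drug should be permanently stopped". Recurrent pneumonitis at the reduced level also ends treatment.

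The stopping event is described in two other places. Section 5.1 refers to GVHD or "any other toxicity caused by idelalisib or placebo causes discontinuation", with a differential above 10%. Section 8.2 cites Section 6 but describes a differential above 10% in toxicities of every kind.

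The Section 6 rule recommends a safety review if the posterior probability that the Arm A TLT rate exceeds the Arm B rate by 0.10 is at least 75%. Both arms have Beta(0.10, 0.90) priors, and looks come every 15 patients.

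**The concern.** The TLT is the quantity behind the precision statement for the safety objective, and it is the only input to the trial's quantitative stopping rule. It should therefore capture the worst outcomes of the toxicities the protocol already expects. As worded, it may not. An uncomplicated grade 3 event of an unlisted type always counts, while a grade 5 event of a listed type counts only if the interruption limb catches it, and that limb is a count of days off drug. A patient who dies soon after the hold, or whose drug is stopped close to day +270, may never accumulate those days.

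At stake are the count in each arm and, in a 45-patient trial with few expected events, whether the review boundary is crossed.

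**Working it through.** **1. Score individual cases against the two limbs.** The second limb can be read in two ways. By type, any event with a Section 5.2 rule is exempt at every grade. By severity, only thresholds that lead to a hold and possible restart or dose reduction are exempt, so events that go straight to a permanent stop count.

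| Case | Interruption >14 days? | Second limb, by type | Second limb, by severity |
|---|---|---|---|
| First pneumonitis, drug held, death on day 8 | No, 8 days | Exempt | Still exempt: Section 5.2 has no severity tier for a first pneumonitis |
| AST/ALT >20x ULN on day +260, permanent stop | No, if counting ends at day +270 (10 days) | Exempt | Counts |
| AST/ALT >20x ULN on day +150, permanent stop, survivor | Yes (120 days to day +270), unless interruption means only a temporary hold | Exempt | Counts |
| Unlisted grade 3 event | Not needed | Counts | Counts |

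The first row is the firmest gap. It closes only if the scorer treats death as an unending interruption, which the text does not say. The late gap covers holds starting on or after day 270 − 14 = +256. That is 14/180 = 7.8% of a 180-day course.

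**2. Sensitivity of the rule to one event.** Inputs (Section 6): Beta(0.10, 0.90) priors, margin 0.10, cutoff 0.75, and looks at Arm A/Arm B = 10/5, 20/10, 30/15. The posterior in each arm is Beta(0.10 + x, 0.90 + n − x), and the rule evaluates P(pA − pB > 0.10). With no TLTs in Arm B:

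| Look (A/B) | Triggers | One event fewer |
|---|---|---|
| 10/5 | 3/10: 0.90 | 2/10: 0.71 |
| 20/10 | 4/20: 0.84 | 3/20: 0.66 |
| 30/15 | 5/30: 0.80 | 4/30: 0.63 |

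At each look, one uncounted Arm A event at the boundary takes the result below 0.75.

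**3. Effect on the probability of triggering (illustration).** Exact enumeration of the rule at three looks, with 5% in Arm B:
- Arm A counted at 5%: 1.9%.
- Arm A counted at 8%: 7.7%.
- Arm A counted at 10%: 14.2%.

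So if 3 to 5 percentage points of Arm A events went uncounted, with none in Arm B, the probability would be 1.9% instead of 7.7% to 14.2%. The 3 to 5 points are an assumption.

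These are not the plan's printed figures. Table 1 gives 1.3% at (0.05, 0.05), 6.8% at (0.05, 0.10) and 32.4% at (0.05, 0.20). The stated inputs give 1.9%, 14.2% and 58.6% with three looks, or 1.5%, 10.6% and 46.2% with two. That mismatch is a separate matter and does not affect the reading of the definition.

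**4. Size of the pool of listed-type events.** Section 5.1 gives serious hepatotoxicity 14%, serious or severe diarrhea 14% and pneumonitis below 5%. Assuming independence, and that these rates carry over to this trial:
- First two: 1 − 0.86 × 0.86 = 26.0%.
- Adding pneumonitis at 5%: 1 − 0.86 × 0.86 × 0.95 = 29.7%.

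That is about 8 to 9 of 30 Arm A patients. It is an upper pool, not the number missed.

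**The case against.** The exemption looks deliberate. Section 6 presents the monitoring as an addition to the allowed dose reductions and aims it at other events. That explains leaving manageable listed toxicities out; it does not explain leaving out deaths from them.

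Several stronger inferences are tempting, and the documents do not support them:

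- A reader might infer that any permanent stop for a listed toxicity scores as no event. A survivor taken off drug for good with more than 14 days left is ordinarily off it for more than 14 days and meets the first limb. Section 5.2 does use separate words for holding and for stopping permanently, but nothing confines interruption to a temporary hold.
- A reader might infer that the exemption certainly applies at every grade. A permanent stop is not a de-escalation, so extreme liver values and life-threatening diarrhea can be read as counting under the second limb.
- A reader might extend the exemption to colitis. The listed term is loose stools or diarrhea, and a grade 3 colitis could count.
- A reader might infer that the missing events fall mainly in Arm A. Section 5.2 says these toxicities also occur in transplant recipients generally, and no placebo rate is given. Grade 3–4 rash, about 21% at 150 mg BID in Section 5.1, has no Section 5.2 rule, so not all known idelalisib toxicities are exempt.
- A reader might take 26–30% as the missed share. Most of that pool may already be caught by the 14-day limb. Section 5.1 also puts mean time to diarrhea at 7.2 months, longer than the roughly six-month course.

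Other safeguards exist: toxicities are summarized by grade and type, non-relapse mortality is estimated, deaths are reportable, and the Safety Monitoring Committee may recommend termination. These make it likely that the events would be seen. None of them enters the posterior calculation.

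**Conclusion.** The concern holds in a limited form. The TLT definition in Sections 4 and 6 has no grade ceiling on its exemption and does not say whether death or permanent discontinuation counts. Read by type, a listed toxicity that is fatal within 14 days of the hold is scored as no event. So may be one that stops drug within about 14 days of day +270, if counting ends there. For a first pneumonitis, the fatal case remains open even on the severity reading. Sections 5.1 and 8.2 add two further descriptions of the stopping event that do not match Section 6.

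The size of any bias cannot be stated, because the documents give neither the share of listed events that would be missed nor their rate on placebo. What can be stated is the rule's sensitivity: with no Arm B events, one uncounted Arm A event at the boundary reverses the recommendation at each look (0.90 to 0.71 at the first). This rests on the printed priors, margin and cutoff. Because the definition feeds the safety objective and the only quantitative stopping rule, and the remedy is a change of wording, it should be corrected.

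**What to change.** In Sections 4 and 6, keep the two existing limbs and add a third: any grade 5 adverse event, and any permanent discontinuation of study drug (idelalisib or placebo) for an adverse event through day +270, is a TLT whatever its type and however few days remain. Reword the stopping-rule descriptions in Sections 5.1 and 8.2 so that they refer to this definition. No dose rule, and no rule for stopping treatment in a patient, changes.

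The cost is a protocol wording change and one derived variable. The case report form must capture the reason for discontinuation; Section 4.1 lists reasons but does not say they are recorded. TLT rates may be somewhat higher in both arms, so the 10% prior mean and the scenarios in Tables 1 and 2 of Section 6 should be rechecked under the new definition.
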